6.3 IBD-BOOST Study Schedule

IBD-BOOST OPTIMISE		Within 1 week of completing checklist	Within 10 weeks of consent/ 2 weeks of trial team receiving the calprotectin result	Within 4 weeks of checklist and calprotectin data sent to clinical team	Within 3 months of checklist and calprotectin result reviewed	3 months after checklist and calprotectin result reviewed	Before study closure
Time Point	Т0	T1	T2	Т3	T4	T5	T6
Screening and invite sent	Х						
Participant Information Sheet	Х						
Consent Form	Х						
Checklist	Х						
Stool sample kit sent to participant		Х					
Calprotectin result received and uploaded by central research team			X				
Checklist and calprotectin result reviewed by patient's local IBD team				Х			
Medical Management Optimisation (if required)					X		
Participant reported Outcome Questionnaire completed (only if management provided)						X	
Clinician Qualitative Process Evaluation Interviews							Х

6.4 Faecal Calprotectin tests

Faecal Calprotectin results will be obtained by posting sample kits to participants after the checklist has been completed. The kits will include a standard and widely used faecal sample pot, and packaging and postage will be compliant with 2004 Human Tissue Act. The envelope will have pre-paid postage. The pot sample will be labelled with the participant's study ID only. No identifying information will be sent to the laboratory at King's College Hospital. All samples will be disposed of following analysis. A copy of their result will be

emailed to the participant from a secured NHS email address within 3 weeks of receiving the sample along with an explanation and confirmation that it will be passed on to their IBD team (Appendix 12).

7. DATA ANALYSIS, MANAGEMENT AND PROTECTION

7.1 Data analysis

The percentage of patients requesting help with their symptoms who report at least one treatable cause will be estimated. The percentage of patients with each treatable cause will be estimated among all those seeking help. For those receiving intervention, change in fatigue, pain and incontinence scores will be estimated with confidence intervals.

The change in generic health-related quality of life (EQ-5D-5L) from survey to end of optimisation and the cost of implementing the optimisation algorithm will be evaluated.

We will collect data on all significant health (NHS perspective) resource inputs associated with optimising medical management. This will include hospital visits, diagnostic procedures, medication. The intervention-specific cost (email, telephone contacts, and tests) will be calculated based on the records (by nurses and doctors) of their interactions with patients. Unit costs from national sources will be applied to estimate patient-level total healthcare costs.

Free text comments from participants gathered in the questionnaire at 3 months (Appendix 6) and from nurses/clinicians (Appendix 5) will be subjected to a simple thematic analysis to determine views on feasibility and any changes suggested.

7.2 Data management

Live data will be stored on a secure database held by the Pragmatic Clinical Trials Unit (PCTU), Queen Mary University of London. Participants completing the checklist and outcome measure via an online link will input their data directly into the database. Paper copies will be received and stored securely at the central research team office or another designated office at King's College London or at LNWUH Trust. Pseudonymised data will be stored for 10 years as per the sponsor's requirement and then securely destroyed. This is stated in the PIS.

All interviews will be digitally recorded, anonymised, professionally transcribed verbatim and analysed using, if appropriate, NVivo8 software for data management. The interview data will be analysed by the qualitative researchers independently in researcher's offices and at the University site (King's College London). Anonymised transcripts will be stored on a password protected computer at King's College London. Audio files will be sent via the KCL secure file transfer service to a KCL approved transcriber who will delete their copy of the audio file and the electronic transcription once the latter has been returned to the research team. The transcriber will remove all identifiable data and render the interviews anonymous. Participants are advised of this in the Participant Information Leaflet. All original and transcribed interview data files will be password protected on computers (e-copies) and physically filed (hard copies) in a locked cabinet at the University site.

Audio files of interviews will be deleted at the end of the programme (planned for November 2023) and confirmation of destruction will be recorded. All other data arising from this study electronic or paper format will be kept for a period of ten years for data management governance as required by the sponsor.

7.3 Data protection and confidentiality of participants

The online checklist and outcome measure will be administered on the REDCAP system or by paper copy and then inputted manually by the central research team. Queen Mary University of London's London Barts Cancer Research UK Centre (QMUL BCC) IT Security is responsible for the security of the QMUL REDCAP service. Any data entered is securely stored at PCTU safe haven (BCC) in their Enterprise level data centres. Data will be backed up daily. Access to the system for data entry staff requires a user account, which will be issued and controlled by the PCTU Data Management Team. All data analyses will be conducted using only the unique study ID. Transfer of data will occur through strong encryption.

Data from the IBD-BOOST Optimise study may be used to support other research (in line with the applicable national regulatory standards) in the future and may be shared anonymously with other researchers as stated in the PIS and consent form.

8. ETHICS

8.1 Ethics favourable opinion, HRA approval and NHS R&D

The Chief Investigator will obtain approval from a recognised NRES Research Ethics Committee & the Health Research Authority (HRA). The study must be submitted for assessment of capacity and capability at each participating NHS Trust using the HRA/REC approved study document set and Statement of Activities (SoA) & Schedule of Events (SoE). The Chief Investigator will require a copy of each participating site's confirmation of capacity and capability, agreed statement of activities, PI & research teams current CV and GCP certificates, before accepting participants into the study. The study will be conducted in accordance with the recommendations for physicians involved in research on human subjects adopted by the 18th World Medical Assembly, Helsinki 1996 (including later revisions) and any other relevant ethical guidance.

8.2 Amendments

On obtaining a favourable ethical opinion and HRA approval, any subsequent changes to the study conduct, design or management will be notified to the original approving REC & HRA and any other relevant regulatory authority via the UK Amendment process (http://www.hra.nhs.uk/research-community/during-your-research-project/amendments/). Authorisation will be sought from the study Sponsor for any future substantial and nonsubstantial amendments arising during the course of the study, prior to submission to the relevant Research Ethics Committee and HRA. Changes to the study will not be implemented until REC/HRA approval has been obtained unless the clinical need warrants this, for example when urgent safety measures are required. The Chief Investigator or designee will work with sites (R&D departments at NHS sites as well as the study delivery team) so they can put the necessary arrangements in place to implement the amendment to confirm their support for the study as amended. NHS R&D Amendment continuation of capacity and capability will be sought (where applicable) from the participating sites before any substantial changes can be implemented at the applicable site. Details of consent procedures are addressed above. An annual progress report will be submitted to the Sponsor and the approving REC/HRA by the CI.

9. STUDY CONDUCT RESPONSIBILITIES

9.1 Assessment and management of risk

This study has been assessed by the Pragmatic Clinical Trials Unit (PCTU) at Queen Mary University of London (QMUL) and it has been found to be a low risk study, as all care will be given by the subject's routine clinical care team and there are no tests or interventions suggested in the algorithm that are not part of routine clinical care. There is potential for participants to become distressed when thinking about their symptoms: the previously completed survey includes a link / website address to Crohn's & Colitis UK who provide support via their helpline, and contact details are included in the Participant Information Sheet. Whilst we do not expect any adverse events to occur in this study, in the unlikely event that any do occur the appropriate reporting procedures will be undertaken and followed up accordingly (see below Section 9.7).

The study will be entered for adoption on to the National Institute for Health (NIHR) Portfolio. All participating sites will be required to follow any applicable procedures outlined by the NIHR and PIs are responsible for uploading recruitment figures in the specified recruitment reports to the Chief Investigator's designated Data Support Coordinator.

9.2 Confidentiality

The Chief Investigator will preserve the confidentiality of participants taking part in the study and will work in accordance with the Caldicott Principles, Data Protection Act 2018, NHS Code of Confidentiality and any relevant NHS Trust organisational policies or Data Protection legislation. Participating NHS sites will be bound to act in accordance with these applicable regulations.

9.3 Indemnity

The Study is sponsored by the LNWUH NHS Trust; the NHSLA Indemnity scheme will cover the study.

9.4 Sponsor

LNWUH NHS Trust will act as the Sponsor for this study and will adhere to the UK Policy Framework for Health & Social Care Research 2017 and any amendments or subsequent replacements. Delegated responsibilities will be agreed with participating NHS Trusts via the statement of activities.

9.5 Funding

The study is funded by the NIHR Programme Grants for Applied Research funding stream.

9.6 Audits and inspections

As this is a low risk study, there will be no planned monitoring for sites. However, where there are any deviations or breaches to the study protocol or research procedures or other concerns for a site, triggered monitoring visits may be conducted at the CI's request by the Quality Assurance team at the PCTU at Queen Mary's University of London. Participating

NHS sites are required to comply with any requests for monitoring by the PCTU or the Sponsor or applicable site R&D Office and ensure that the study documentation and information is available. Copies of audit / monitoring reports should be sent to the Sponsor's R&D office. Protocol deviations, non-compliances, or breaches from the approved protocol must be reported immediately to the Sponsor R&D Office.

9.7 Safety

Adverse events (AEs): AE are any clinical change, disease or disorder experienced by the participant during their participation in the study, whether or not considered related to the use of the intervention being studied.

Serious adverse events: An AE is defined as serious (an SAE) if it results in one of the following outcomes:

- A life-threatening AE
- In-patient hospitalisation or prolonged hospitalisation not related to IBD flares, which are expected events
- Persistent or significant disability/incapacity
- A congenital anomaly/birth defect in the offspring of a subject
- Is otherwise considered medically significant by the investigator
- Other medical events requiring intervention to prevent one of the above outcomes.

Follow-up after SAEs: An SAE occurring to a research participant should be reported to the main REC where in the opinion of the Chief Investigator (CI) the event was:

- Related that is, it resulted from administration of any research procedures and
- Unexpected that is the type of event is not listed in the protocol as an expected occurrence

The Chief Investigator or Sponsor will complete and send a SAE report for non-ctimps (clinical trial of investigational medical products) to the REC within 15 days of becoming aware of the event.

After a SAE, a decision will be made by the study team, after advice from the relevant authorities and the participant's IBD team, as to whether the participant should be withdrawn from either the study. However, we do not envisage a situation, except death, in which a participant would need to be withdrawn.

Arrangements will be made by the study team for further assessment and management as agreed with the relevant authorities, IBD team, GP and participant.

The investigator will provide the study team with a 1-month follow-up report on all SAEs. Further monthly reports should be provided in the absence of resolution. These reports will be communicated to the Programme Steering Committee, REC, and to the local R&D office. Blank Adverse Event Forms (Sponsor's standard form) will be distributed to sites that are recruiting.

AEs that do not require reporting: Expected AEs include planned/elective hospitalisations, or unplanned but expected hospitalisation due to flare-up of IBD: these are expected during the course of the study and will not be collected as SAEs.

Stopping rules

The study may be prematurely discontinued by the Sponsor or Chief Investigator on the basis of new safety information or for other reasons given by the Steering Committee or REC concerned. The study may also be prematurely discontinued due to lack of recruitment or on advice from the Programme Steering Committee (if applicable), who will advise on whether to continue or discontinue the study and make a recommendation to the Sponsor. If the study is prematurely discontinued, active participants will be informed and no further participant data will be collected.

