1.3 The need for research

It is currently unclear how best to manage these common symptoms of fatigue, pain and urgency/incontinence in people with inflammatory bowel disease. Many patients do not report these symptoms at all, or if they do are offered little beyond investigation and treatment of active disease. We have found in previous work that many patients do not receive what are considered "standard care" investigations or management for these symptoms (8).

Our previous systematic literature reviews (9-12) have identified many potentially reversible causes for these symptoms. Many of these, particularly the psycho-social elements, will be addressed in our online self-management programme which follows on from the current proposal within our programme grant. However, there are also "medical" causes (such as anaemia as a cause of fatigue), which could be addressed before patients enter a self-management programme. However, during extensive consultation with expert clinicians during development of the current checklist and algorithm, there is genuine equipoise over whether patients need these medical causes addressing, whether it is likely to make any difference to symptoms, or whether they should be able to directly access online self-management (the RCT in the next stage of our programme).

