The nurse/clinician will initially review the patient's responses to the checklist, the result of a faecal calprotectin test and the medical notes and decide if the patient is clearly in remission and has no "red flags" or other issues which need investigating, according to the algorithm. Some participants will at this point clearly have no need for further action and be eligible for entry into the RCT for self-management (separate to the current application). Others will need a follow up phone call to clarify some issues, or need a face to face review with the nurse/clinician, or immediate onward referral to medical colleagues (if they have "red flags" which warrant urgent medical attention).

Depending what these enquires reveal, the nurse will then initiate appropriate management for any abnormalities found which may be causing symptoms (such as active IBD disease or anaemia). If tests or new management are initiated, the nurse will determine, using clinical judgement, whether to see the patient face to face or follow up via telephone or email. S/he will review the patient or the results of tests as necessary and decide when the patient's symptoms have been "optimised", over the following 3 months, while recognising that in IBD not all biomedical abnormalities and disease activity may be resolvable. The management initiated will be standard care treatments (as agreed during our consensus process) and not any novel interventions outside of standard care. Tests ordered, their results and management initiated will be recorded after each activity on a study Case Report Form (CRF) (Appendix 5; IBD-BOOST Medical Management Optimisation CRF).

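### Section 9.7 exempts all planned or elective admissions from SAE collection, so a non-flare elective admission arranged after consent for a new or worsened condition meets the SAE definition but is not collected

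*Protocol*

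**What the plan says.** All the rules that matter are in Protocol section 9.7.

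- **AE definition.** "AE are any clinical change, disease or disorder experienced by the participant during their participation in the study", whether or not it is thought related to the intervention.
- **SAE hospitalisation bullet.** An AE is serious if it results in "In-patient hospitalisation or prolonged hospitalisation not related to IBD flares, which are expected events". Flares are the only exception stated there.
- **Exemption.** The paragraph on AEs that need no reporting states: "Expected AEs include planned/elective hospitalisations, or unplanned but expected hospitalisation due to flare-up of IBD". It continues: "these are expected during the course of the study and will not be collected as SAEs".
- **REC reporting.** An SAE goes to the main REC only if the Chief Investigator considers that it meets both of two conditions. One is about cause: "Related that is, it resulted from administration of any research procedures". The other turns on the protocol's own list of expected events: "Unexpected that is the type of event is not listed in the protocol as an expected occurrence".

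Two other sections give context. Section 1.4 says that some participants will need "immediate onward referral to medical colleagues", and ties this to red flags that call for urgent attention. Section 1.3 says that "there is genuine equipoise over whether patients need these medical causes addressing".

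**The concern.** A definition and its exemption should exclude the same events. The flare exception does this, because it appears in both places. The exception for planned or elective admissions appears only in the later paragraph. It carries no condition on the reason for the admission or on whether it was arranged before or after the participant joined.

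What is at stake is which serious events reach safety oversight. Section 9.7 sends one-month follow-up reports on all SAEs to the Programme Steering Committee, the REC and the local R&D office, and allows the study to be stopped on new safety information. An event that is not collected as an SAE enters neither route. Section 9.6 plans no routine site monitoring, so nothing else in the plan would regularly bring such an event to light. The study tests a process of looking for and acting on medical causes, so an admission for a new problem after enrolment is an event that the overseers could reasonably want to see.

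**Working it through.** The point is textual. The plan gives no figure to reproduce and no formula applies. The check is to run each kind of admission through the AE definition, the SAE bullet and the exemption in section 9.7.

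| Admission | AE and SAE wording | Exemption paragraph | Result |
|---|---|---|---|
| Unplanned, not flare-related | SAE | Not exempt | Collected; consistent |
| Unplanned, flare-related | Excluded by the bullet | Exempt | Not collected; consistent |
| Planned, flare-related | Excluded by the bullet | Exempt | Not collected; consistent |
| Elective, non-flare, for a pre-existing condition that has not changed | Usually not an AE, as there is no clinical change during participation | Exempt | Not collected; no real conflict |
| Elective, non-flare, arranged after consent for a new or worsened condition | AE, and SAE by the hospitalisation bullet | Exempt | Meets the definition but is not collected |

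Only the last row is a mismatch.

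The REC step follows from the same listing:

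1. REC reporting needs an SAE that is both related and unexpected.
2. Unexpected means that the type of event is not listed in the protocol as expected.
3. Planned or elective hospitalisation is listed as expected, whatever its cause or date.
4. So an admission in the last row fails the second condition even if the Chief Investigator judges it to have resulted from a research procedure.

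The last check is whether the event would be recorded elsewhere. Section 6.2 has the Optimisation CRF record contacts, tests, results and the management started within the algorithm. Section 7.1 collects hospital visits and diagnostic procedures for costing. Either could pick up some of these admissions. An admission arranged later by another team after a referral is not clearly within the CRF's scope, and no text passes the costing data to safety oversight.

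**The case against.** The strongest reply is that this is a deliberate exception and not an error. It stands under its own heading, which presupposes events that would otherwise count, and its instruction not to collect is explicit. A site that reads the whole section knows what to do. This largely stands: it would go too far to say that section 9.7 contradicts itself for every elective admission or that sites will be left with two opposite instructions. For an unchanged pre-existing condition the AE definition is not met, so nothing conflicts. What remains is that the exception reaches further than the definition and takes in a class of events that the definition treats as serious.

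A reader might also infer that the exemption hides admissions produced by the algorithm's own referrals. The documents do not support that. The onward referral in section 1.4 is immediate and for urgent red flags, and an unplanned non-flare admission that followed it would still be an SAE. Nothing in the protocol text at hand says that the algorithm leads to elective admissions, and the algorithm itself (Appendix 3) is not shown. The equipoise in section 1.3 is about whether causes need addressing and whether symptoms would change. It does not raise a safety question.

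Other points on that side have weight. A serious condition behind an elective admission could still be reported under the SAE bullet for events that the investigator considers medically significant, although that depends on individual judgement. Section 9.1 rates the study as low risk, with only routine-care tests and interventions. The study has a single group, and its primary outcome is the proportion with potentially treatable contributors, so no estimate or comparison changes.

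**Conclusion.** The point holds in a narrow form and is minor. The exemption in section 9.7 is wider than the SAE definition, and the gap is one class of event: non-flare elective admissions arranged after consent for a new or worsened condition. These meet the AE and SAE wording, are not collected as SAEs, and cannot reach the REC because they are listed as expected.

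The size cannot be derived, because the documents give no rate of elective admission. For scale only, each 1% of the 200 planned participants would be 0.01 × 200 = 2 people. It would be tempting to add that an SAE count of zero would be misread as evidence of a low admission rate. The protocol plans no such estimate, so that reading has no basis in the document.

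The conclusion assumes that the AE definition is applied as written and that the exemption covers elective admissions arranged at any time, since it states no limit. It does not assume that the algorithm causes any admission.

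**What to change.** In section 9.7, limit the exemption for planned or elective hospitalisations to those arranged before consent, or for a pre-existing condition unchanged since consent. Keep the existing exclusion of IBD-flare admissions, planned or unplanned, as it is. Reword the hospitalisation bullet of the SAE definition to carry the same exceptions, so that the definition and the exemption exclude the same events.

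Non-flare admissions arranged after consent for a new or worsened condition would then be reported on the existing Adverse Event Form. They would no longer be listed as expected, so one judged related could go to the REC. A tick box for whether the admission arose from the checklist or algorithm review is optional, and would let the study team answer the question that the documents leave open.

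The change affects reporting only and alters no clinical management. It costs one clause in section 9.7, a matching edit to one bullet, possibly one box on an existing form, and a few more SAE forms.
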